3.2 Secondary Objectives & Hypotheses

(1) **Objective:** Based on changes in tumor FDG uptake at 3 weeks, determine which patients have FDG “flare” (an early increase in tumor FDG PET/CT uptake), and assess whether FDG “flare” is predictive of progression-free survival and overall survival in patients with melanoma on pembrolizumab.

Hypothesis: A flare response on FDG PET/CT performed 3 weeks after initiation of pembrolizumab is predictive of progression-free survival and overall survival in patients with melanoma.

(2) **Objective:** To collect tumor tissue pre- and post- treatment with pembrolizumab for correlation with changes in FDG uptake and objective response to therapy, and for studies of mechanism of action of PD-1 blockade with pembrolizumab.

Hypothesis: Treatment with pembrolizumab will result in a measurable change in tumor immune biomarkers, which will correlate with changes in tumor FDG uptake (including a “flare” response) and objective response to therapy, and will contribute to a better understanding of the mechanism of action of pembrolizumab.

(3) **Objective:** To measure immune biomarkers in blood from subjects before and at serial time points after treatment with pembrolizumab, for correlation with changes in FDG uptake and objective response to therapy, and for studies of mechanism of action of PD-1 blockade with pembrolizumab.

Hypothesis: Treatment with pembrolizumab will result in a measurable change in blood immune biomarkers, which will correlate with changes in tumor FDG uptake (including a “flare” response) and objective response to therapy, and will contribute to a better understanding of the mechanism of action of pembrolizumab.

(4) **Objective:** To correlate changes in tumor FDG uptake (including a “flare” response), serum immune biomarkers, and tissue immune biomarkers with objective response to therapy, progression-free survival, and overall survival. Changes in FDG uptake within immune related tissues (lymph nodes, spleen, bone marrow, and thymus) will also be correlated with serum and tissue immune biomarkers, and response.

Hypothesis: Serum and tissue immune biomarkers provide additional predictive value regarding objective response to therapy, progression-free survival, and overall survival when combined with FDG PET/CT imaging data.

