4.1.2.2 Secondary Endpoints

Progression free survival (PFS), is defined as the time from initiation of Pembrolizumab to documented disease progression, death due to any cause or last patient follow-up that documented lack of disease progression.

Overall survival, is defined as start date of Pembrolizumab until death from any cause or last patient contact alive. Survival data will be obtained from the electronic medical records.

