7.1.2.2 Tumor Imaging and Assessment of Disease

The following procedures will be done at each imaging session, as per routine clinical practice for FDG PET/CT imaging.

- Injection of FDG performed as per routine clinical procedure.

All women of child-bearing potential will be asked on the day of the PET/CT scan if they might be pregnant; this is a standard question for all patients who will be undergoing PET/CT scans due to the radiation exposure associated with the scan. If the patient is unsure about whether she might be pregnant then a urine pregnancy test will be performed prior to the injection of FDG.

The patient will be made comfortable in a preparatory room. Approximately 15 mCi of FDG will be administered according to the standard procedures used for clinical FDG PET/CT at the Hospital of the University of Pennsylvania. All patients will undergo a vertex of skull to toes PET/CT scan starting at approximately 60 minutes after FDG injection. A brief low-dose CT scan will be acquired according to standard PET/CT imaging procedures; this is used for attenuation correction and anatomical localization of findings in the PET scan. This can be performed either before or after the PET transmission scan. There are no separate diagnostic CT scans performed as part of this research.

A total of three FDG PET/CT exams will be performed as follows:

- Baseline: A restaging FDG PET/CT will be obtained no more than 4 weeks prior to initiation of pembrolizumab to assess baseline, pre-therapy tumor glycolytic activity. This exam will be obtained for study purposes, although in some cases it may be obtained as clinical standard of care for restaging of disease prior to initiation of a new line of therapy. If this exam is obtained as clinical standard of care, it may occur prior to consent and enrollment in this study.
- 1st Post-therapy: at approximately 3 weeks (\pm 3 weeks) following the start of pembrolizumab, a post-therapy FDG PET/CT will be obtained. This exam will be obtained for study purposes, to assess glycolytic activity at sites of metastatic disease at an early time-point.

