7.1.4.2 Clinical Follow-up

Clinical follow-up may include standard of care imaging, tumor markers and standard visits with a treating physician at intervals standard for metastatic melanoma follow-up after the start of new treatment, and usually at the time of symptomatic progression. The timing of clinical visits will be determined by the treating physician and is not mandated by this study.

Information will be collected through medical record review to assess for status of disease and the date of progression will be documented at the time of clinical progression. Clinical follow up for overall survival, by medical record review, will continue until loss to follow up or death. For those whose are cared for by a non-UPHS clinician during this period, this clinician will be contacted by phone for follow-up. The patients may also be contacted by phone for follow-up.

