8.0 STATISTICAL CONSIDERATIONS

8.1 Design:

This is a pilot correlative study for patients with metastatic melanoma receiving pembrolizumab on a standard regimen. The intent of this study is to evaluate FDG PET/CT as an early measure of response to immunotherapy. Tumor FDG uptake will be measured at baseline and at 3 and >10 weeks after initiation of pembrolizumab. 30 evaluable patients will be enrolled; evaluable implies that the patient had baseline and week 3 FDG PET/CT scans. This study will also include serum and tissue sampling for immune biomarkers.

8.2 Objectives:

The primary objectives are to:

1. Determine the distribution of changes from baseline in tumor FDG uptake on PET/CT at 3 weeks and >10 weeks after initiation of pembrolizumab.
2. Test for the association between change in tumor FDG uptake on PET/CT at 3 weeks and objective response (RECIST).

The secondary objectives are to:

1. Based on change in FDG uptake at 3 weeks, determine which patients have FDG “flare.”
2. Test for the association between FDG flare (yes/no) and objective response.
3. Test for the association between FDG flare and progression-free and overall survival.
4. Test for correlation between change in FDG uptake and levels of immune biomarkers in serum and tissue.
5. Test for association between changes in immune biomarkers in serum and tissue with objective response, progression-free survival, and overall survival.

8.3 Endpoints:

1. Objective response is defined by RECIST. The clinical evaluation takes place at 3 months per standard pembrolizumab regimens. Patients will be categorized as responders (complete response or partial response) or nonresponders (stable disease or progressive disease).

2. The maximum standardized uptake value (SUVmax) will be analyzed for all tumor sites. Immune-related tissues will be analyzed with SUVmax and SUVmean.
3. Studies have shown that the baseline test/re-test variability is 15-20%. Thus, FDG “flare” will likely be defined by >20% increase in tumor FDG uptake at 3 weeks. This definition may be modified for the observed distribution of changes in tumor FDG uptake on our study.
4. Progression-free and overall survival are defined in Section 4.1.2.
5. Immune biomarkers (see Section 7.1.2.3).

8.4 Plans for Data Analysis:

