This is a pilot correlative study of FDG PET/CT imaging to evaluate early response to immunotherapy. We will first begin with a descriptive analysis. For continuous variables, we will generate graphs and descriptive statistics (e.g., means, standard deviations, medians and inter-quartile range). Categorical variables will be described by frequencies, proportions and 95% exact confidence intervals. Change in tumor FDG uptake will be closely examined. It is likely that change in tumor SUVmax >20% will be classified as a FDG “flare” and the number of patients with a flare will be computed.

Next, associations between change in tumor FDG uptake with clinical outcomes will be conducted. Change in tumor FDG uptake at 3 weeks will be compared between responders and nonresponders by a two sample t-test. Also, objective response rates will be compared between patients with or without FDG “flare” by Fisher’s exact test.

PFS and OS will be estimated by the method of Kaplan and Meier. Median values and 95% confidence intervals will be calculated. PFS and OS will be compared between patients with or without FDG “flare” by the log rank test. Cox regression may be used to assess the effect of continuously scaled measurements of FDG change. For all survival analyses, a landmark analysis will be performed. Here, PFS or OS are defined from a landmark, which is 3 weeks after initiation of pembrolizumab. The landmark method is necessary because the change in tumor FDG uptake is known at 3 weeks. Serum and tissue biomarkers will be correlated with change tumor FDG uptake, using Pearson correlation or Spearman’s correlation, as appropriate. Within-patient pre-/post-treatment changes in biomarkers will be evaluated by paired Student’s t-test or Wilcoxon signed ranks test, as appropriate. We will test for an association between post-/pre-treatment fold change in immune biomarkers in serum and tissue and objective response, progression-free survival, and overall survival using logistic regression (for response) and Cox regression (for time-to-event outcomes) using landmark survival analysis.

8.5 Sample Size Justification:

The target is 30 evaluable patients, which may require up to 35 enrolled patients. Based on our clinical experience, we assume a 50% objective response rate, thus there will be 15

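### The survival landmark is fixed at week 3, but the scan that defines FDG flare may be done as late as week 6

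*Combined protocol and SAP*

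**What the plan says.** Section 8.4 prescribes a landmark analysis for all survival comparisons: "Here, PFS or OS are defined from a landmark, which is 3 weeks after initiation of pembrolizumab". Its only stated reason is that "The landmark method is necessary because the change in tumor FDG uptake is known at 3 weeks".

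The scan that supplies the FDG change is scheduled "at approximately 3 weeks (\pm 3 weeks) following the start of pembrolizumab" (section 7.1.2.2; the same window appears in section 2.1 and the section 6.1 flow chart). The permitted range is therefore week 0 to week 6.

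Three other provisions bear on the point:

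- **Evaluability** (section 8.1): "evaluable implies that the patient had baseline and week 3 FDG PET/CT scans". The patient need not be progression-free at the scan.
- **PFS** (section 4.1.2.2): "the time from initiation of Pembrolizumab to documented disease progression, death due to any cause", or last follow-up without progression.
- **Dating of progression** (section 7.1.4.2): by record review, "the date of progression will be documented at the time of clinical progression". It can therefore be dated before a late scan.

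Section 8.4 also applies landmark survival analysis to the "post-/pre-treatment fold change in immune biomarkers in serum and tissue", without saying which post-treatment sample is meant. Section 3.2, objective 4, looks for added predictive value for "progression-free survival, and overall survival when combined with FDG PET/CT imaging data".

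No section moves the landmark to the scan date, limits the survival analyses to scans done by week 3, or treats flare as time-dependent.

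**The concern.** A landmark analysis is valid only if the grouping variable is known for every patient at the landmark and cannot be altered by what happens afterwards. That holds here for scans up to week 3 and fails for scans in weeks 3 to 6.

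Take a patient who progresses clinically at week 4 and is scanned at week 5. The patient is event-free at week 3 and so enters the analysis. The event counts as post-landmark. The growing tumour may raise SUVmax by more than 20% and so earn the flare label. The event has then helped to define the group whose event rate is being tested. For such patients the flare-PFS comparison, a secondary objective, cannot separate flare predicting progression from progression raising the uptake. The landmark was introduced to prevent exactly this.

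The bias pushes the flare hazard ratio above 1. Sections 4.1 and 8.5 expect larger FDG changes in responders, so against that expectation it would tend to mask a favourable association. Section 3.2 states no direction for the survival hypothesis, so a spurious adverse association is also possible.

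**Working it through.** **Plan's own figure.** The only power statement is 84% for the primary t-test (section 8.5). With 15 per group, a 1.0 SD difference and one-sided 5%, the noncentral t (28 df, noncentrality √(15/2) = 2.74) gives 84.8%, so it reproduces. It does not involve the landmark. No power or event count is given for PFS or OS.

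**Inputs.** From the plan: landmark week 3, scan window weeks 0-6, 30 evaluable patients, flare as a rise of more than 20%. The plan gives no median PFS, no distribution of scan times and no flare rate. These are assumptions:

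- exponential PFS with median 3, 6 or 12 months (13, 26 or 52 weeks);
- no true prognostic effect of flare;
- flare probability 20%, rising to 40-60% if progression precedes the scan.

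**Step 1: patients exposed.** With hazard h = ln 2 / median, P(event in weeks 3-6, given event-free at week 3) = 1 − exp(−3h).

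| Median PFS (weeks) | Probability | Per 30 patients |
|---|---|---|
| 13 | 14.8% | 4.4 |
| 26 | 7.7% | 2.3 |
| 52 | 3.9% | 1.2 |

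Only events before the patient's own scan contaminate the comparison. Averaged over scans uniform on weeks 3-6, the probability is 1 − (1 − exp(−3h))/(3h), or 2.3, 1.2 and 0.6 patients per 30. With scans uniform on weeks 0-6 it is half that: 1.1, 0.6 and 0.3.

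**Step 2: the mechanism by hand, worst case.** All scans at week 6, median 13 weeks, flare 60% against 20%:

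- Flare patients: 0.148 × 0.6 + 0.852 × 0.2 = 0.259, of whom 0.089/0.259 = 34% have their event in weeks 3-6.
- Non-flare patients: 0.148 × 0.4 + 0.852 × 0.8 = 0.741, of whom 0.059/0.741 = 8% do.

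The whole difference is an artefact, and it sits in the first three weeks after the landmark.

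**Step 3: spurious PFS hazard ratio.** Cox model, 1,000,000 simulated patients per scenario, ranges over the medians and flare probabilities above:

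| Scan timing | Week-3 landmark, progression documented when it occurs | Week-3 landmark, late documentation |
|---|---|---|
| Uniform, weeks 0-6 | 1.015-1.089 | 1.005-1.017 |
| Normal (mean 3, SD 1.5), truncated to weeks 0-6 | 1.008-1.070 | 1.001-1.013 |
| All at week 6 | 1.053-1.359 | 1.012-1.083 |

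Late documentation assumes that a quarter of pre-week-12 events are recorded when they occur and the rest at about week 12. This is prompted by restaging after week 10 (section 2.1) and evaluation at 3 months (section 8.3). A week-6 landmark, or delayed entry at the later of week 3 and the scan, gives 0.99-1.01 throughout.

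**Step 4: at the trial's size.** A log-rank simulation with n = 30, baseline flare 30%, and 60-90% after progression gave median observed/expected hazard ratios of 1.04-1.25 at week 3 and 0.99-1.04 at week 6. With no contamination the week-3 values were 1.01-1.05. With 90% flare after progression, the two-sided null rejection rate was 6.6-12.8% at week 3 and 6.0-7.2% at week 6, against about 6-8% uncontaminated.

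**Step 5: precision.** For illustration, take 6 flare among 27 patients, all with events. SE(log HR) = 1/√(27 × 6/27 × 21/27) = 0.46, and exp(1.96 × 0.46) = 2.5.

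**Step 6: OS.** A patient must be alive to be scanned, whether or not flare is found, so the guaranteed survival after week 3 is common to both groups (mean 0.75 week with uniform scans, 3 weeks with all at week 6). The simulated null hazard ratio is 0.998-1.004.

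**Step 7: biomarkers.** Week-1 and week-3 bloods fit a 3-week landmark. It would be invalid for bloods at weeks 6 to 15 or 1 year, or for a biopsy after week 3. The biopsy follows the scan by up to 7 days, so to about week 7, and later is not a deviation. If a biomarker shifts 0.5 SD at progression (an assumption), the spurious hazard ratio per SD is 1.00 for week-1 or week-3 samples, 1.02-1.07 for week 6 and 1.07-1.18 for week 15. It is 1.00 with the landmark at sampling.

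**The case against.** The inconsistency itself is hard to dispute. The serious objection is that it matters little.

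- **Size.** With spread scans the bias is at most about 9%, in a pilot whose interval spans a factor of 2.5 each way. A check at n = 30 with 60% against 20% flare found rejection rates of 8.2-10.6%, against 7.5-8.6% without contamination. Clear inflation (10-20%) needed every scan at week 6 and progression documented at once. This stands and sets the weight of the point.
- **Stacked extremes.** The 1.36 needs all scans at the window limit, 3-month median PFS and 60% flare after progression. The protocol aims at about week 3, and a 3-month median sits uneasily with its assumed 50% response rate. This also stands: 1.36 is a bound, not an expectation.
- **Assumed inputs.** The documents do not supply the 40-60% against 20% contrast, and section 4.1 expects basal tumour glycolysis to change little over the interval. Under section 5.3 some patients who progress may be discontinued before the scan and never become evaluable, which would reduce the contamination. Both are fair, but neither makes flare known at week 3.
- **Primary test.** If progression raises uptake before a late scan, it also enters the t-test and the Fisher comparison. That is correct. Only the landmark rule leaves them untouched, and changing it will not address that route.
- **Biomarkers.** Any error there depends on a sample choice the plan has not made. That is true, which is why the request is only to name the sample.

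**Conclusion.** The concern holds. The reason given for the 3-week landmark is untrue for any scan done in the second half of the permitted window, and no other section repairs it. This is a wrong rule as written, not missing detail.

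The consequence is confined to the secondary survival analyses and is probably modest: a spurious PFS hazard ratio of about 1.01-1.09 with spread scans, nearer 1.00-1.02 if most progression is documented at about week 12, and up to 1.36 only in the extreme case. These figures rest on the assumed PFS medians, scan timing, documentation pattern and flare probabilities. The null OS comparison shows no differential bias. The plan should be corrected because the bias is avoidable at little cost; it does not threaten the study.

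**What to change.** In section 8.4, replace the 3-week FDG landmark with one of the following:

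- **Week 6**, the end of the scan window. This is simple, but it does not cover a scan done after the window. About 1 to 4 of 30 patients leave the PFS risk set, or 1 or fewer if most progression is first documented at about week 12.
- **Delayed entry**: keep time from the start of pembrolizumab and let each patient enter at the later of week 3 and the actual scan date. This also covers out-of-window scans and drops only patients whose event or censoring precedes their own entry.

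Add a sentence naming the post-treatment sample for the biomarker survival models. Week-1 or week-3 bloods can keep the 3-week landmark. For any later sample, place the landmark at or after collection. Models that combine biomarkers with FDG should use the later of the two landmarks.

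Report how many patients are excluded for an event or censoring before the landmark or entry time.

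The cost is one sentence for FDG and one for biomarkers, with no new visits or data. Later biomarker landmarks lose more of the patients event-free at week 3: 4-15% at week 6, 11-38% at week 12 and 15-47% at week 15, under the same assumed PFS medians. That favours an early sample.

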7.1.2.3 Tumor Tissue Collection and Correlative Studies Blood Sampling

For patients participating in the Penn Melanoma Tissue Collection Program (UPCC #08607, IRB #703001), blood samples will be collected, processed, and stored according to the program's standard operating procedure. Currently, this includes drawing less than 65 mL of blood according to the following schedule (after initiation of pembrolizumab): weeks 0, 3, 6, 9, 12, 15, and at 1 year. For the purposes of this study, patients will have an additional sample of blood drawn at approximately 1 week after starting pembrolizumab; this sample will also be collected, processed, and stored according to the Penn Melanoma Tissue Collection Program standard operating procedure. If patients have not consented to participate in the Penn Melanoma Tissue Collection Program, then no blood samples will be drawn for the purposes of this study. Analysis of blood samples will include, but is not limited to, analysis of serum cytokines, chemokines, and T cell markers; proposed cytokines and chemokines are listed in Table 1, and proposed T cell markers are listed in Table 2. This data will be correlated to patient response as well as changes in tumor FDG uptake. Some of these studies will be performed upon receipt of additional funding. There may be patients for which some or all of these blood draws are not possible, in this case it will be documented in the CRF and the blood draws may be omitted and it will not be considered a protocol deviation. Experimental pathology results will not be reported to the participant and will have no impact on the treatment decisions made by the treating physician.

Patients may undergo tumor biopsy as part of their clinical care prior to initiation of pembrolizumab. For patients participating in the Penn Melanoma Tissue Collection Program, these pre-therapy tissue samples will be collected, processed, and stored according to the program's standard operating procedure. For the purposes of this study, patients will have a post-therapy tumor biopsy which will be scheduled within 7 days after the 1st Post-therapy

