FDG PET/CT; this tissue will also be collected, processed, and stored according to the Penn Melanoma Tissue Collection Program standard operating procedure. If patients have not consented to participate in the Penn Melanoma Tissue Collection Program, then no tumor biopsies will be performed for the purposes of this study. The biopsy techniques preferred for this study include core biopsies or surgical biopsies. The same biopsy techniques should be used as routinely used for a given tumor lesion/location. When possible, the post-therapy tumor biopsy should target the same lesion that was biopsied pre-therapy; if the original lesion cannot be biopsied, then a lesion with a significant change in FDG activity should be targeted for biopsy. Analysis of tissue samples will include, but is not limited to, analysis of tumor-infiltrating lymphocytes (TILs), macrophages, and other myeloid subsets; changes in tumor cells will also be evaluated, and the fraction of necrotic cells will be calculated. TILs will be analyzed using multiparameter flow cytometry; proposed phenotypic markers are listed in Table 2. This data will be correlated to patient response as well as changes in tumor FDG uptake. Some of these studies will be performed upon receipt of additional funding. There may be patients for which a pre- or post- therapy tumor biopsy is not performed; those cases will be documented in the CRF and will not be considered a protocol deviation. In some cases tissue may be collected outside of the 7 day window following the 1st Post-therapy FDG PET/CT; this will not be considered a protocol deviation. Experimental pathology results will not be reported to the participant and will have no impact on the treatment decisions made by the treating physician.

For patients participating in the Penn Melanoma Tissue Collection Program, we will follow the standard operating procedure regarding archival tissue access for patients undergoing a biopsy or surgery on melanoma or other skin cancer for diagnosing, treating or research purposes, but for which there is no applicable left over fresh tissue, or patients who had a biopsy or surgical procedure done on melanoma or other skin cancer for diagnosing, treating or research purposes at the University of Pennsylvania Health System (UPHS) or at an institution outside of UPHS. If patients have not consented to participate in the Penn Melanoma Tissue Collection Program, then no archival tissue will be requested.

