Chemokines	Inflammatory Cytokines	Inhibitory Cytokines
Mip1a	IFNg	IL4
Mip1b	TNF	IL10
Rantes	IL1	TGFbeta
IP10	IL2	
ITAC	IL6	
Fractalkine	IL12 IL17 IL23	

Table 1. Proposed cytokine / chemokine analysis.

Lineage Markers	Differentiation	Transcription Factors	Inhibitory Receptors	Function
CD3	CD27	Tbet	PD-1	Granzyme B
CD4	CD45RA	Eomes	Tim3	Ki67
CD8			LAG-3	Perforin
FoxP3			CD160	
CD14			CTLA4	
CD16			KLRG1	
CD19			SAP	
			CD244	
			TIGIT	

Table 2. Proposed flow cytometric analysis.

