responders and 15 nonresponders. A comparison of change in FDG SUV at 3 weeks between responders and nonresponders, will have 84% power to detect a 1.0SD difference in mean values, using 1-sided two sample t test at a 5% significance level. The 1-sided test is justified, since responders are expected to have greater changes in FDG SUV.

8.6 Study Duration:

This study will enroll 30 evaluable patients over 1 year.

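### The secondary immune-biomarker objectives plan roughly 160 to 315 significance tests with no error control, key marker or hypothesis-generating label

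*Combined protocol and SAP*

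**What the plan says.** Section 8.2 lists two biomarker items among the secondary objectives: correlation of immune biomarkers in serum and tissue with change in FDG uptake, and association of biomarker change with objective response, PFS and OS. Section 8.4 gives the methods. Pearson or Spearman correlation serves the first and logistic and Cox regression the second, with paired tests for the change from before to after treatment. On response the text reads: "We will test for an association between post-/pre-treatment fold change in immune biomarkers in serum and tissue and objective response". Section 3.2 attaches hypotheses to these objectives: that biomarkers will change, that the change will correlate with FDG change and response, and that biomarkers add predictive value to imaging.

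The markers are in Section 7.1.2.3. For blood, "proposed cytokines and chemokines are listed in Table 1, and proposed T cell markers are listed in Table 2". For tumor, "TILs will be analyzed using multiparameter flow cytometry; proposed phenotypic markers are listed in Table 2". The caption "Table 1. Proposed cytokine / chemokine analysis" shows that the panel is provisional, and the section says that some of the work depends on further funding.

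The only significance level in the plan is in Section 8.5, for the comparison of FDG change between responders and nonresponders, "using 1-sided two sample t test at a 5% significance level". The documents name no key biomarker, testing order, multiplicity adjustment, false discovery rate or significance level for the biomarker tests. Section 7.1.5 uses the word exploratory for the tumor-by-tumor analysis and for uptake in immune-related tissues, but nothing applies it to the blood and tissue markers.

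**The concern.** Each secondary biomarker hypothesis is worded about biomarkers in general, not about a named marker. With dozens of candidates, four outcomes per candidate and no rule for what counts as support, a single small p-value anywhere in the table could be presented as confirming the hypothesis. Section 4.1 expects the study to help identify predictors of response and to inform combination strategies, so a chance finding could be carried into later work.

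The blood schedule adds to this. Samples are planned at week 0 and at seven later times (weeks 1, 3, 6, 9, 12 and 15, and one year). Section 8.4 does not say which later sample enters the fold change, so the time point could be chosen after the results are seen.

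**Working it through.** **The plan's own figure.** Section 8.5 assumes 15 responders and 15 nonresponders ("The target is 30 evaluable patients, which may require up to 35 enrolled patients"; "we assume a 50% objective response rate") and states "84% power to detect a 1.0SD difference in mean values". For a one-sided 5% t-test with 28 degrees of freedom and noncentrality 1/√(1/15 + 1/15) = 2.74, the noncentral t distribution gives 84.8%. The stated 84% is reproduced. It covers one comparison, and the plan gives no corresponding figure for the biomarkers.

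**Marker count.**
- Table 1: 6 chemokines + 8 inflammatory cytokines + 3 inhibitory cytokines = 17.
- Table 2: 7 lineage + 2 differentiation + 2 transcription factors + 9 inhibitory receptors + 3 function = 23.

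**Tests per marker.** Four association tests (FDG change, response, PFS, OS). A fifth is added if the paired pre/post test is counted.

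**Number of tests at one post-treatment time point, and expected false positives (tests × 0.05) if every null is true.**
- Table 1 in blood and Table 2 in tissue only: (17 + 23) × 4 = 160; 8.0. This is the literal reading of serum and tissue in Sections 8.2 and 8.4.
- Table 2 in both blood and tissue, lineage markers left out as gating markers (an assumption): (17 + 16 + 16) × 4 = 196; 9.8.
- Table 2 in both blood and tissue, as Section 7.1.2.3 describes: (17 + 23 + 23) × 4 = 252; 12.6.
- The same with paired tests: 63 × 5 = 315; 15.75, about 16.

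Combining the literal reading with removal of the lineage markers would go lower: (17 + 16) × 4 = 132; 6.6. Testing all seven later blood samples would go much higher: (40 × 7 + 23) × 4 = 1,212; about 61.

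**Chance of at least one false positive.** If the tests were independent, 1 − 0.95^160 = 99.97% and 1 − 0.95^252 is above 99.99%. Markers are correlated, so simulation was used as well:
- With 252 null tests in 30 patients, the chance is about 99% at a marker correlation of 0.6 and about 92% at 0.8.
- If a single common factor drives all 63 markers at correlation 0.6, the chance for one outcome is 57.2%. Over four independent outcomes that is 1 − (1 − 0.572)^4 = 96.6%, and somewhat less because PFS and OS overlap.

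**Spread.** Correlation leaves the expected number unchanged but makes the actual number erratic. For 252 independent tests the 95% range is 6 to 20. At correlation 0.6 it is about 1 to 36.

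**Possible corrections.**
- Bonferroni over 252 tests: 0.05/252 = 0.0002. A two-sided t-test at that level, 15 against 15, has about 10% power for a 1.0 SD difference.
- Benjamini-Hochberg at q < 0.10, run separately in three panels (serum, blood flow, tissue flow) for each of four outcomes, makes 12 families. If every null is true, the chance of at least one false call is 1 − 0.9^12 = 72% if independent, and still about 53% to 56% at correlation 0.6.
- Benjamini-Hochberg over all association tests as one family: about 10% or less.

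**The case against.** The strongest defence is the study's own framing. The trial phase is given as correlative, and Sections 8.1 and 8.4 both call it a pilot correlative study. Strict familywise control would be out of place and would remove almost all power. Biomarker results do not affect treatment, and the primary objectives do not depend on them. All of this stands, and it limits the weight of the point and the kind of remedy. It does not close the gap: the plan separates exploratory work from secondary objectives and places the blood and tissue biomarkers among the latter, with hypotheses.

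Three stronger statements are tempting, and the documents do not support them. A reader might infer that every marker will be judged at an unadjusted 5%. The plan sets no level or decision rule for these tests, so 5% is an assumption. A reader might take 252 tests and a dozen false positives as the plan's count. The panels are proposed, partly dependent on funding, and open to several readings, and a dozen is the expectation only if no association is real. A reader might also conclude that the hypotheses would be supported whatever the truth. Nothing in the plan says that one nominal p-value counts as support.

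Nor is 30 the biomarker sample size. It is the target for patients with both PET scans. Blood and biopsy need consent to the tissue collection program, and either may be omitted.

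**Conclusion.** The concern holds as a gap in the secondary analysis plan. At one post-treatment time point, the tables and objectives imply about 160 to 315 tests in at most 30 evaluable patients, and fewer where samples are missing. At an assumed 5% per test and with every null true, 8 to 16 false positives are expected. The expectation does not need independence, but the actual number could be far from it. At least one false positive is near certain under every reading from 160 tests up with independent or moderately correlated markers, and remains likely at stronger correlation. Fewer would occur if some associations are real. The conclusion does not depend on which count is preferred: the biomarker hypotheses could readily appear supported by chance, and the plan gives readers no means of telling whether they were. The consequence is confined to how secondary results are interpreted and reported.

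**What to change.** In Section 8.4:

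- Name one post-treatment blood time point for the fold change, and use it for the correlation with FDG change too. The choice needs to be compatible with the 3-week landmark for PFS and OS in the same section.
- Report Benjamini-Hochberg q-values beside the raw p-values, treating all biomarker association tests as one family. Splitting by panel and outcome would lose most of the protection, as shown above.
- Call a marker associated only at a pre-stated q, for example below 0.10.
- Label all other biomarker results, including other time points and the paired tests, hypothesis-generating, and give estimates with confidence intervals.

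The cost is a paragraph of text and a few lines of code, settled before the biomarker data are analyzed. No sample or marker is added or dropped. The downside is that fewer markers will be called associated. It is a cheap improvement.
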